#### Analysis Populations

All participants selected for analyses must have completed the whole study. Any participants with data that inexplicably varies widely from the rest of their treatment group will be excluded from analyses.

In addition, any of the following will be considered a major protocol violation:

- Violation of inclusion or exclusion criteria that are deemed to affect efficacy.
- Non-compliance with assigned treatment regimen.
- Use of prohibited treatment or medication before or during the study, which is felt to affect the assessment of efficacy.
- Not receiving randomised treatment.

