- Operations involving metal implants, plates, clips, stents, bands or expanders
- Operations within the previous 8 weeks
- Kidney problems
- Have had liver transplant or waiting for a liver transport
- Fits, blackouts, or epilepsy
- Piercings, hearing aids, dentures (to check if they are removable)
- Medication patches, tattoos, permanent eyeliner or makeup

For female participants:

- Chance of pregnancy
- Breast-feeding
- Intrauterine contraceptive device (IUD)

For cases of operations, implants, or devices a surgeon's report will be requested from the participant's medical records, which will then be reviewed by the radiologist at NNUH before proceeding with the MRI scan.

If participants are unable or unwilling to undergo an MRI scan, they are still able to participate in other components of the study.

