#### 6.5 Withdrawal of Participants

Participants may be withdrawn from the study for the following reasons:

- At their own request
- If continuation of the study would be detrimental to their wellbeing
- Adverse Event (AE) or Serious Adverse Event (SAE)
- Non-compliance
- Loss of mental capacity of consent

As soon as the research team became aware that a participant had lost the capacity to consent or has met one of the exclusion criteria, then that participant would be fully withdrawn from the study such that no further samples nor cognitive assessment data would be collected. As we are targeting healthy volunteers with no diagnosis of dementia or neurological condition, the loss of capacity during the study is extremely unlikely.

If a participant is prematurely withdrawn from the study for any reason after product administration, the investigator must make every effort to perform these Follow-Up Visit assessments: Review of concomitant medications, and review adverse events. This information should be recorded in the case report form. In all cases, the reason for withdrawal must be recorded in the case report form.

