# 10. Data Analysis

Statistical Analyses

For each outcome measure, data will be manually screened and (only) data deemed 'invalid' will be omitted from analyses. Data will be deemed invalid if a biological rational sustains this assumption, e.g. non physiological values. These invalid data and the reason for exclusion will be reported in the final report.

Parametric statistical analyses will be performed, except where normality cannot be achieved, in which case equivalent non-parametric analyses will be performed.

Demographic, behavioural and biological (neuro-imaging, clinical and biochemical) data will be analysed using the Statistical Package for the Social Sciences (SPSS; v16.0), applying standard statistical thresholds (p<0.05), corrected for multiple comparisons where appropriate.

The impact of treatment on the outcomes of interest will be established using repeated measures ANOVA with time and treatment as independent variables. Individual means will be obtained for each outcome measure and group means, collapsed across the treatment arms, will be calculated to

determine treatment effects. Relationships between lifestyle, cognitive, biochemical and cardiovascular variables, and establishment of the main determinants of the response to intervention will be performed using correlation and regression analysis

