# 11. Handling of Tissue

A suitably qualified member of the research team will obtain a 22ml venous blood sample at the initial screening visit and 32ml again at each of the baseline and follow-up visits. Someone competent in taking blood samples will undertake the collection of blood. Blood will be collected

and temporarily stored at CRF during clinic visits, then transported and stored long-term at the Norwich Research Park Biorepository.

If participants consent to having stool samples collected, these samples will be collected as close to the study as possible, within 48 hours. Participants will be provided with the necessary equipment including the sample jar, collection plate device, freezerbag, and gloves. Participants will be provided with an information form with clear instructions outlining how to collect and store the sample. Collection of these samples will be conducted by a member of the research team upon arrival at each study day. These samples will then be stored in short-term storage freezers at the CRF before transported and stored at the Norwich Biorepository.

If participants consent to having urine samples collected, they will be provided with the necessary equipment for collection including the sample jar and bag. These samples will be usually collected during the screening and follow-up research clinic visits. These samples will then be transported and stored long-term at the Norwich Biorepository.

The biological samples (including the DNA) collected during the intervention will be kept at the Norwich Biorepository for up to 10 years as the samples could be invaluable for future research in this area. Any subsequent analyses would be conducted in accordance and agreement with local ethical procedures. Volunteers will be asked if they agree to their anonymous samples being stored for future analysis as part of the consenting process.

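### All analyses are limited to participants who completed the whole study, a term left undefined, and no analysis of all randomised participants is named

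*Protocol*

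**What the plan says.** **Who is analysed.** Section 10, Analysis Populations: "All participants selected for analyses must have completed the whole study". No intention-to-treat or all-available-data set appears elsewhere in the protocol. The same section lists non-compliance among major protocol violations, without saying whether a violation removes the person from analysis.

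**What happens on withdrawal.** Section 6.5 lists own request, detriment to wellbeing, adverse events, non-compliance and loss of capacity as reasons. It then makes two separate provisions:
- Anyone who loses capacity or has met an exclusion criterion is "fully withdrawn from the study such that no further samples nor cognitive assessment data would be collected".
- For premature withdrawal for any reason after product has been taken, every effort is to be made to perform these "Follow-Up Visit assessments: Review of concomitant medications, and review adverse events". No microbiome, cognitive or imaging outcome is listed.

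**What is optional.** Section 6.3 says of people who cannot or will not have MRI that "they are still able to participate in other components of the study". Section 11 makes stool collection conditional: "If participants consent to having stool samples collected". Section 12.5 tells participants that they need not consent to every part of the study.

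**Size.** Section 6 recruits 60 people, 30 per arm. The Power Calculation also assumes 30 per arm, so nothing is allowed for attrition.

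**The concern.** Randomisation makes the arms comparable at entry. Selecting people on what happens afterwards can undo that. Tolerability of a twice-daily powder may differ between cranberry and placebo, so adverse-event withdrawal and non-compliance may differ by arm. Section 6.3 excludes people with diagnosed gastrointestinal or psychiatric disorders and significant memory complaints. These lie close to the trial's own outcomes, gut microbiota and cognition. A participant who came to meet such a criterion would leave the study, and therefore the analysis, for a reason linked to what is being measured.

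This is more than a detail left to a statistical analysis plan. The protocol fixes the population outright, so a plan that analysed everyone randomised would contradict it. No later plan can recover week-12 outcomes that were never collected.

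The undefined completion rule adds a second risk. Usable microbiome and cognitive data could be discarded because a person declined MRI, in a trial with no spare participants.

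**Working it through.** **1. The provisions side by side**

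| Provision | Where | Consequence |
|---|---|---|
| Completers only | Section 10, Analysis Populations | Anyone withdrawn leaves every analysis |
| Explicit stop on samples and cognitive data | Section 6.5 | Covers lost capacity or a met exclusion criterion only |
| Medication and adverse-event review | Section 6.5 | Covers any premature withdrawal after product; no outcome is planned, but none is forbidden |
| MRI, stool and other parts optional | Sections 6.3, 11, 12.5 | A person may finish all visits without every component |
| Three visits define participation | Sections 5 and 7 | Supports reading completion as reaching the follow-up visit |

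**2. The plan's own figure**

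The Power Calculation gives an FDR of 0.5% to 4% at 30 per group, with half the features null and at least 80% power. It states no effect size or per-feature alpha, so the figure cannot be reproduced independently. It can be inverted:

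FDR = p0·α / [p0·α + (1 − p0)·power]. With p0 = 0.5 and power = 0.8, α = 0.8·FDR / (1 − FDR).

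- FDR 4%: α = 0.032 / 0.96 = 0.0333. For 80% power at 30 per arm (two-sided, noncentral t), d = 0.782. The normal approximation gives 0.767.
- FDR 0.5%: α = 0.004 / 0.995 = 0.0040. The normal approximation gives d = 0.96.

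**3. Power if fewer are analysed** (α and d held as above; the loss rates are assumptions)

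| Analysed per arm | Loss | Power, 4% FDR end | Power, 0.5% FDR end |
|---|---|---|---|
| 30 | 0% | 0.80 | 0.80 |
| 27 | 10% | 0.75 | 0.74 |
| 24 | 20% | 0.70 | 0.67 |

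These treat individuals as independent, although Section 7.2 assigns dyads.

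**4. Bias from analysing completers**

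If a share q leaves one arm, that arm's completer mean differs from its full mean by q × (mean of stayers − mean of leavers). Assume q of 10-20% and leavers 0.5-1.0 SD worse:

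- lowest: 0.10 × 0.5 = 0.05 SD
- highest: 0.20 × 1.0 = 0.20 SD

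A simulation checks this (20,000 trials, no true effect, 30 per arm, dropout in one arm correlated 0.3 or 0.5 with the outcome):

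| Dropout in one arm | Correlation | Bias (SD) | Type I error |
|---|---|---|---|
| 10% | 0.3 | 0.06 | 5.3% |
| 10% | 0.5 | 0.10 | 6.5% |
| 20% | 0.3 | 0.11 | 6.6% |
| 20% | 0.5 | 0.17 | 10.1% |

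For scale, the standard error of a difference between arms at 30 each is √(2/30) = 0.26 SD.

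**5. The literal reading of completion**

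If every component were required and losses were independent, 10% dropout, 10% without MRI and 5% without stool would leave 60 × 0.90 × 0.90 × 0.95 ≈ 46. With 20%, 20% and 10%, 60 × 0.80 × 0.80 × 0.90 ≈ 35 would remain. All these rates are assumed.

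**The case against.** Four points can fairly be made in the plan's defence.

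**Outcome collection is not banned for every withdrawal.** A reader might infer from Section 6.5 that all outcome data stop whenever someone withdraws. The text does not say so. The explicit stop covers lost capacity or a met exclusion criterion. For other withdrawals the section lists a minimum and does not prohibit more. This stands, but no week-12 outcome is planned for those people either, and the completer rule would exclude them even if one were obtained.

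**The all-components reading is the harshest available.** A reader might infer that declining MRI or stool removes a person from every analysis. Section 6.3 keeps people without MRI in the rest of the study, Section 12.5 permits partial consent, Section 10 screens data outcome by outcome, and Missing and Spurious Data expects missing values to be marked and explained. Completion most naturally means reaching the follow-up visit. What remains is that the term is undefined and the literal reading is open.

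**The exclusion criteria carry qualifiers.** The gastrointestinal disorder must be existing and diagnosed, the psychiatric disorder clinically diagnosed and the memory complaint significant. Few healthy volunteers may come to meet them in 12 weeks. This stands on frequency. Adverse events and non-compliance remain as routes out.

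**The magnitudes are assumed, and the title calls the study a feasibility intervention.** Both are true. The lower half of the bias range is small beside a standard error of 0.26 SD. But the objectives and the Statistical Analyses section set out treatment effects between arms, and that comparison should rest on the randomised groups.

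**Conclusion.** The concern holds in limited form. The protocol confines every analysis to completers, names no analysis of all randomised participants, and allows withdrawals that can depend on arm or outcome. It also leaves completion undefined while making components optional. It does not support the claims that outcome collection is forbidden after every withdrawal, or that people without MRI or stool will certainly be dropped.

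Neither the size nor the direction of any bias can be derived from the documents. The 0.05-0.20 SD illustration rests on assumed one-arm dropout of 10-20% with leavers 0.5-1.0 SD worse. The fall from 80% to about 70% power rests on an assumed 20% loss, the 4% end of the FDR range, a two-sided test and independent individuals. The case for change rests on the stated rule rather than on these figures, and it is best made before follow-up visits because uncollected outcomes cannot be restored.

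**What to change.** **Section 10, Analysis Populations.**
- Make the primary analysis all randomised participants in the arm assigned. Each outcome uses everyone with that measurement, whether or not they complied or completed other components. This also removes the need to define completion for the primary analysis.
- For continuous outcomes, use a likelihood-based model with baseline and week 12 both as outcomes, so that people with baseline only still contribute. With a single post-baseline visit, a model that takes baseline only as a covariate would still drop anyone without week-12 data.
- For the microbiome community analyses in Section 8.5 (PERMANOVA, LEfSe, Random Forests), which such a model does not cover, use all available samples by assigned arm and report missingness by arm.
- Keep the completer or per-protocol set as a sensitivity analysis, with completion defined.

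**Section 6.5.** State that stopping the product is not in itself leaving the study, so that the already planned week-12 outcomes can be sought from people who stop product and still consent. The sponsor should reconcile this with the rule against further samples and with withdrawals for wellbeing, leaving those rules and the reasons for stopping product unchanged.

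**Cost.** Amendment wording, some week-12 assessments in people who would otherwise not have been followed, and a little more analysis. Including people who did not take the product dilutes the efficacy estimate slightly; the per-protocol sensitivity analysis shows by how much. The model still assumes that missingness is explained by observed data, which is a further reason to seek week-12 outcomes where the rules allow.

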#### Missing and Spurious Data

Where appropriate, missing values will be marked and explained in individual data tables. When one or more outliers are defined, scientific evidence or explanations will be provided to justify the exclusion of the subject's data from the statistical analysis. In case of outliers, the corresponding statistical analysis will be provided with and without these values.

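### The protocol excludes participants who differ inexplicably from their own arm, which contradicts its two other exclusion rules and raises type I error by an amount set by an unstated cut-off

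*Protocol*

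**What the plan says.** Section 10 of the protocol has three rules on leaving data out.

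- **Analysis Populations:** "Any participants with data that inexplicably varies widely from the rest of their treatment group will be excluded from analyses". The unit is the participant and the reference is that participant's own arm. The trigger is a wide departure with no explanation.
- **Statistical Analyses:** "For each outcome measure, data will be manually screened and (only) data deemed 'invalid' will be omitted from analyses". The test of invalidity is "Data will be deemed invalid if a biological rational sustains this assumption, e.g. non physiological values", and "These invalid data and the reason for exclusion will be reported in the final report". The unit is the data for one outcome measure.
- **Missing and Spurious Data:** where outliers are defined, "scientific evidence or explanations will be provided to justify the exclusion of the subject's data from the statistical analysis". It adds: "In case of outliers, the corresponding statistical analysis will be provided with and without these values".

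Treatment effects are tested by repeated measures ANOVA with time and treatment as factors, "applying standard statistical thresholds (p<0.05), corrected for multiple comparisons where appropriate". Non-parametric equivalents are used where normality cannot be achieved. The planned size is 30 per arm.

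**The concern.** There are two problems.

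The first is a conflict in the text. A participant whose values are odd for no known reason must be removed under Analysis Populations. The same values may not be removed under Statistical Analyses, because no biological rationale exists, and cannot be justified as Missing and Spurious Data requires. A later analysis plan could choose among the rules, but the protocol's mandatory sentence would still stand.

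The second is statistical. Removing people because their outcome lies far from the centre of their own arm makes each arm look more homogeneous than it is, and the test then treats the remaining data as complete. False positive results become more likely and intervals too narrow. With no cut-off fixed, how far this goes depends on whoever decides what counts as wide. A participant with a genuinely large or absent response could also be lost, and the protocol plans to study the determinants of response.

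**Working it through.** **1. Can the three rules be followed together?** Take a plausible but extreme value with no known cause.

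| Heading in section 10 | Condition for removal | Met? | Consequence |
|---|---|---|---|
| Analysis Populations | Inexplicably far from own arm | Yes | Participant is excluded |
| Statistical Analyses | Biological rationale for invalidity | No | Value stays |
| Missing and Spurious Data | Evidence or explanation supplied | No | Exclusion not justified; if made, both analyses are shown |

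The first row contradicts the other two. The unit also differs between the first and second rows: participant against outcome measure.

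**2. Inputs for the error rate.**
- From the protocol: 30 per arm, threshold 0.05, two time points.
- With two time points, the time-by-treatment test equals a two-sample t-test on change, t = (m1 − m2) / [s_p √(1/n1 + 1/n2)].
- Assumed, because the protocol gives none: a cut-off of c SDs from the arm mean, applied once, with c = 3, 2.5 or 2. Data have no true effect.

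**3. The plan's own figure.** With no exclusion and normal data the test is exactly 5% by theory. Simulation of 40,000 trials gave 4.8%, with Monte Carlo standard error √(0.05 × 0.95 / 40,000) = 0.11 points.

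**4. Why own-arm trimming matters.** For a normal variable cut at ±c SD, the remaining variance is 1 − 2cφ(c)/[2Φ(c) − 1] of the original.
- c = 3: 1 − 0.0266/0.9973 = 0.973, so the SD is 0.987 of its true value.
- c = 2.5: 1 − 0.0876/0.9876 = 0.911, so the SD is 0.955.
- c = 2: 1 − 0.2160/0.9545 = 0.774, so the SD is 0.880.

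The denominator of t shrinks accordingly. Because the limits move with each arm's own mean, the difference between the trimmed means does not shrink with it. Limits common to both arms pull both means towards one centre, which restores the balance.

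**5. Simulated type I error, normal data, t-test.**

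| Cut-off | Own arm | Pooled, blind to arm | Mean removed of 60 (own arm) |
|---|---|---|---|
| 3 SD | 5.4% | 4.9% | 0.07 |
| 2.5 SD | 6.6% (6.8% in a second run) | 4.8% | 0.5 |
| 2 SD | 10.2% | 5.2% | 2.4 |

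**6. Skewed data.** A t-test on single raw log-normal values gives 8.9% to 11.0% at these cut-offs, but that is not what the protocol plans for such data. The non-parametric fallback gave 6.5% to 7.7% in 10,000 trials; runs of 8,000 trials gave 5.6% to 7.0%. Tests on change gave about 5.4% to 7.2%. Pooled trimming stayed at about 5%. A different rule can do more: 1.5 × IQR within arm, with the rank test on log-normal values, gave 11.4% in one run of 8,000.

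**7. The missing outcome.** The rule does not say on which outcome a participant must be unusual. If any of 10 outcomes counted, at 2.5 SD (0.51 of 60 flagged per outcome, independence assumed), the expected loss is 60 × [1 − (1 − 0.51/60)^10] ≈ 4.9 of 60. Correlated outcomes would give fewer.

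**The case against.** The best defence reads the sentence as shorthand, to be operated through Missing and Spurious Data. Every outlier exclusion would then come with a justification and an analysis that keeps the values, so nothing is hidden. This stands in part: a reader might infer undisclosed exclusions, and the protocol does not support that. The mitigation is incomplete. Analysis Populations does not refer to the with-and-without rule and neither version is named as primary. The sentence also sits in the definition of the analysis population, which makes the trimmed set the natural default. Nor can an exclusion that is inexplicable supply the explanation required.

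A second objection concerns size. At 3 SD with normal data the excess is under half a point. The 10.2% needs a 2 SD cut-off, a strained reading of wide variation because it removes about 2.4 of 60 participants from perfectly normal data. This stands. It would be wrong to say that the rule doubles the error rate, or to quote 8.9% to 11.0% for biomarkers, given the planned switch to non-parametric tests.

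Third, a reader might infer that applying the rule breaks the blind. It does not have to: coded group labels are enough. The defect is that arm-blind judgement is not required.

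Fourth, it is tempting to say that true strong or absent responders will be deleted. That depends on the unstated cut-off, and the analysis with the values included would still show them.

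**Conclusion.** The contradiction is certain from the text and needs no assumption: the rule under Analysis Populations cannot be followed together with the rules before and after it.

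The direction of the statistical effect is also clear, and it comes from the reference to the participant's own arm: the same cut-offs on pooled data keep the error near 5%. Its size is conditional on cut-offs that I had to assume. With 30 per arm and normal data it is 5.4%, 6.6% and 10.2% at 3, 2.5 and 2 SD. For skewed data under the planned non-parametric test or a test on change it is about 5.4% to 7.7% at those cut-offs.

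This should be fixed. It does not by itself invalidate the trial, which describes itself as a feasibility intervention and already promises results with outliers included.

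**What to change.** - Delete the sentence on participants who vary from their treatment group from Analysis Populations.
- Keep one removal rule, that of Statistical Analyses: only measurements, not participants, that are invalid on a documented reason are removed. Decide this on pooled data, blind to arm, before the code is broken.
- Under Missing and Spurious Data, name the analysis that keeps all other outliers as primary and the analysis without them as sensitivity.

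A narrower repair would keep statistical outlier exclusion but make it subject to the other two rules, judged on pooled data blind to arm, with one version named as primary. That also holds the error near 5%, but it still needs a stated cut-off.

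The cost is one deleted sentence, two short clarifications and a blinded data review. The downside is a somewhat larger residual variance, which reflects the real spread of the data.
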